7.2. Secondary outcomes

The secondary outcomes are as follows:

1. Time to first non-vertebral fracture (ICD-10-SE: S22.2, S22.3, S22.4-S22.8, S32.1-S32.5, S42, S52, S72, S82)
2. Time to first new non-hip, non-vertebral fracture (ICD-10-SE: S22.2-S22.8, S32.1-S32.5, S42, S52, S72.3-S72.4, S82)
3. Time to first hip fracture (S72.0-S72.2)
4. Time to first new forearm fracture (S52)
5. Time to first clinical vertebral fracture (S12, S22.0, S22.1, S32.0, M48.5, M49.5, M80.0A, M80.0J, and M80.0K)
6. Time to death

Study Name: The Fragility Fracture Trial
Version No: 2
Date: 2020-10-04
EudraCT No: 2019-004766-17

7. Time to first new cardiovascular event (stroke or myocardial infarction) (ICD-10-SE: I21, I60-I64)
8. Time to first new cancer diagnosis (ICD-7-SE: 140-209)
9. Occurrence of fall from standing height or less (ICD-10-SE: W00, W01, W03, W04, W18) not resulting in fracture between baseline and 48 months

Hip fractures are included among non-vertebral fractures and forearm fractures are included among non-hip, non-vertebral fractures. However, hip fractures and forearm fractures will also be assessed separately because these are common and classic types of osteoporotic fractures. Fractures, myocardial infarction, stroke, and cancer events will be identified through self-report and verified by investigators through review of medical records. Participants will also have the possibility of reporting these outcomes to their study center between the scheduled study contacts. Participants who withdraw will be asked if they wish to answer questions about these outcomes before they formally withdraw.

In the 10-year follow-up, myocardial infarction and stroke will be traced using the above-mentioned ICD-10-SE codes in the National Patient Register, SWEDEHEART, and the Swedish Stroke Register. SWEDEHEART is a register that covers most patients in Sweden who are hospitalized for acute coronary syndrome, coronary interventions, or valvular interventions.⁴⁵ The Stroke Register is a register of Swedish stroke patients, although it does not have complete coverage of the population.⁴⁶ At the 10-year follow-up, cancer events will be identified through the Swedish Cancer Register, which records all new cases of cancer in Sweden since 1958.⁴⁷ Deaths will be identified through the Swedish Cause of Death Register and by reports from family members to study centers.⁴⁸

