12.5. Data management

The trial statistician will continuously monitor eCRFs for accuracy and completeness (including range and logical checks) and for compliance with this protocol. Any inaccuracies, inconsistencies, or deviations will be reported to the appropriate study center, with a request for a correction or an explanation. The trial database will be backed up regularly. The sponsor/coordinating investigator may also appoint staff to conduct on-site monitoring to verify eCRFs with source documents. A detailed plan for data management has not been developed at the time of writing, but it will be attached to the Clinical Study Report.

13. Statistical Analysis

Statistical analyses will be performed using the latest version of R software. All statistical hypothesis tests that can be two-sided will be two-sided. P-values <0.05 will be considered statistically significant, unless otherwise specified. P-values will be rounded to two decimal places if ≥ 0.01 and rounded to three decimal places if <0.01 but ≥ 0.001 . P-values <0.001 will be expressed as " <0.001 ".

The zoledronic acid and placebo groups will be defined according to randomization. Baseline date will be defined as the date of randomization. Follow-up time will be defined as the date of death, withdrawal, loss to follow-up, or last follow-up contact (whichever came first) minus the date of randomization plus 1 day (to account for the possibility of an event later in the day of randomization). Incomplete follow-up will be defined as follow-up time that ends before the last study contact.

Study Name: The Fragility Fracture Trial
Version No: 2
Date: 2020-10-04
EudraCT No: 2019-004766-17

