13.4. Analysis of follow-up

The number and percent of randomized patients that are contacted at each study contact (visits and telephone interviews) will be reported for the zoledronic acid and placebo groups. The number and percent not completing follow-up will be presented by cause (death, adverse event, loss to follow-up, withdrawal, etc.). Differential follow-up duration between the zoledronic acid and control group will be examined by plotting Kaplan-Meier curves and testing for a difference using the log-rank test. Differences in the number and percent prematurely unblinded will be examined using Fisher's exact test. Number and percent prematurely unblinded by cause (accident, adverse event, or other) will be presented.

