The occurrence of falls will be analyzed as the number and percent of participants reporting at least one fall. Falls will not be analyzed as a time-to-event outcome because participants may not remember exactly when they fell. The zoledronic acid and placebo groups will be compared using relative risks, with 95% confidence intervals estimated based on the normal approximation. Participants with incomplete follow-up and who did not report a fall during follow-up will be assumed not to have fallen.

Change-from-baseline outcomes will be analyzed using analysis of covariance. The response variable will be post-intervention value and the explanatory variables will be baseline value and treatment group. For the EQ-5D-5L exploratory outcomes, which will be measured every 12 months of follow-up, an analysis of covariance will be run with each follow-up value as the post-intervention value. To prevent the problem of multiple testing, the stepwise approach to testing described in Section 13.8 will be used. The assumptions of linearity, constant variance, and normality will be checked using residual plots and normal quantile-quantile plots. Clear violations of these assumptions will be dealt with by transformations of the response variable or its baseline value. Clear violations of the assumption of constant variance may instead be dealt with using the method of weighted least squares. Outliers will not be removed. Participants with missing follow-up data on change-from-baseline variables will be excluded.

The hypothesis tests of efficacy will not be adjusted for multiple testing to avoid a large reduction in the power of the trial.

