13.8. Subgroup, sensitivity, and exploratory analyses

Baseline characteristics and efficacy outcomes will be presented in subgroups defined by type of baseline fragility fracture (grouped by the first 3 characters of ICD-10-SE codes), age (65-74, 75-84, or ≥ 85 year), sex, study center, and FRAX 10-year probability of major osteoporotic fracture. In the efficacy analysis, product terms will be included in regression models to assess interaction of treatment with time since fragility fracture, type of fragility fracture, age, sex, study center, physical activity (mean steps/day), and receipt of one or both infusions. These interaction effects will be tested using Wald tests for numeric and binary variables and likelihood ratio tests for multi-level categorical variables. We do not expect these interaction analyses to show significant differences in effect.

Six sensitivity analyses will be conducted. First, to assess the presence of confounding, regression analyses will be adjusted for the following baseline covariates: age, sex, BMI, study center, time since fragility fracture, and site of fragility fracture (grouped by the first 3 characters of ICD-10-SE code). Second, the efficacy analysis will be rerun in a per-protocol population (i.e., participants who met all eligibility criteria, either died or completed follow-up, and both were qualified to receive and did receive the 2 assigned infusions). Third, efficacy concerning time-to-event outcomes will be analyzed using the Andersen-Gill Cox model for recurrent events.⁶³ Fourth, in the analysis of the primary outcome, the potential effect of informative censoring (including the competing risk of death) will be assessed by rerunning Cox models under the extreme scenarios that all participants who did not complete follow-up either (1) sustained a fracture at the time of censoring (i.e., were at high risk of fracture) or (2) had complete follow-up with no event (i.e., were at low risk of fracture).⁶⁴ Fifth, participants with a history of cancer at baseline will be excluded from the efficacy analysis of new cancers diagnosed during follow-up. Sixth, outcome events not verified by medical records will be included in the efficacy analyses.

Study Name: The Fragility Fracture Trial
Version No: 2
Date: 2020-10-04
EudraCT No: 2019-004766-17

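### Withdrawn and lost participants with no reported fall are scored fall-free to 48 months, which understates fall risk and ties the relative risk to follow-up

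*Protocol*

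**What the plan says.** Reducing falls is the fifth secondary objective (Protocol, Section 3.2). The corresponding outcome is the ninth in Section 7.2, "Occurrence of fall from standing height or less" without fracture, counted from baseline to 48 months.

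Section 13.6 fixes the analysis:

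- The outcome is the proportion reporting at least one fall, with arms "compared using relative risks, with 95% confidence intervals estimated based on the normal approximation".
- Time-to-event methods are ruled out: "Falls will not be analyzed as a time-to-event outcome because participants may not remember exactly when they fell".
- Early leavers are handled by assumption: "Participants with incomplete follow-up and who did not report a fall during follow-up will be assumed not to have fallen".

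The opening of Section 13 shows who falls under that assumption: "Follow-up time will be defined as the date of death, withdrawal, loss to follow-up, or last follow-up contact (whichever came first"), and "Incomplete follow-up will be defined as follow-up time that ends before the last study contact". The rule therefore covers deaths, withdrawals and losses alike.

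Two other provisions touch on early exit. Section 13.4 says: "Differential follow-up duration between the zoledronic acid and control group will be examined by plotting Kaplan-Meier curves", with a log-rank test. Section 13.8 tests extreme scenarios for those who did not complete follow-up, but only for fractures: "Fourth, in the analysis of the primary outcome, the potential effect of informative censoring".

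**The concern.** Falls accumulate with time. A participant who withdraws at month 8 without having fallen has 40 further months in which a fall would go unrecorded, yet enters the analysis as a known non-faller at month 48. This lowers the reported risk in both arms. It also makes the relative risk depend on how long each arm was observed, so a difference in retention can look like an effect on falls, or mask one.

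The protocol itself allows for unequal follow-up, since Section 13.4 tests for it, but nothing in the falls analysis depends on the result.

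The reason given for avoiding time-to-event methods does not require this rule. Table 1 in Section 9 schedules a question about falls at eight contacts, roughly six months apart. The exact date may be forgotten, but the interval is known, and a discrete-time analysis needs no more than that.

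**Working it through.** The protocol states no fall risk, death rate or power for falls, so it has no figure of its own to reproduce here. The check asks what the stated rule returns when zoledronic acid has no effect on falls.

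**Inputs from the protocol**
- 2900 participants randomized 1:1, so about 1450 per arm (Sections 10 and 13.10).
- Planned dropout of 5% overall, deaths excluded (Section 13.10).
- Incomplete follow-up of 4%, 8%, 13% and 17% in the four earlier trials, deaths excluded (Section 13.10).

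**Assumptions**
- True 4-year fall risk F of 30%, 50% or 70%, the same in both arms, with a constant hazard.
- A share q of each arm leaves early, evenly over the 4 years and independently of fall risk.

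**Formulas**
- Chance of a fall before exit among early leavers: Fe = 1 − F / (−ln(1 − F)). This is 0.1589, 0.2787 and 0.4186 for F = 0.3, 0.5 and 0.7.
- Reported risk under the rule: (1 − q)F + qFe.
- Standard error of log RR: √[(1 − pz)/(1450 pz) + (1 − pp)/(1450 pp)], where pz and pp are the reported risks on zoledronic acid and placebo.

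**Worked case, F = 0.5, exit 15% on zoledronic acid and 20% on placebo**
- Zoledronic acid: 0.85 × 0.5 + 0.15 × 0.2787 = 0.4668.
- Placebo: 0.80 × 0.5 + 0.20 × 0.2787 = 0.4557.
- RR = 0.4668 / 0.4557 = 1.024. Standard error of log RR = 0.0401, so the shift in z is ln(1.0243) / 0.0401 = 0.60.

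**Results, true RR = 1**

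| Exit, zoledronic acid / placebo | RR at F = 30% | F = 50% | F = 70% | Chance that the 95% interval excludes 1 |
|---|---|---|---|---|
| 5% / 5% | 1.000 | 1.000 | 1.000 | 5.0% |
| 4% / 6% | 1.010 | 1.009 | 1.008 | 5.3-6.2% |
| 15% / 15% | 1.000 | 1.000 | 1.000 | 5.0% |
| 15% / 20% | 1.026 | 1.024 | 1.022 | 7.1-12.5% |
| 20% / 15% | 0.975 | 0.976 | 0.979 | 7.1-12.5% |

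The shift in z for 15% against 20% runs from about 0.4 to 0.8.

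**Absolute risk.** With F = 50% and equal exit, 5% early exit gives a reported 48.9% and 15% gives 46.7%.

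**Limiting case.** If every early leaver went at time zero, RR = (1 − qz)/(1 − qp), where qz and qp are the exit shares on zoledronic acid and placebo. This is 0.96/0.94 = 1.021 for 4% against 6%, and 0.85/0.80 = 1.063 for 15% against 20%.

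**Standard error.** In 4000 simulated trials of the worked case, the empirical standard deviation of log RR was 0.0395 and the mean estimated standard error was 0.0401.

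**The case against.** Four points on the other side deserve an answer.

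**Deaths.** A reader might infer that the rule also misrecords people who die. The documents do not support that. Someone who dies at month 8 without falling has, in fact, no fall by month 48, and Section 7.2 defines the outcome as occurrence in that period. If all 15% of early exits were deaths, the 46.7% above would be the true proportion who ever fell. Mortality still shortens the time at risk and so affects the comparison, but that is an estimand choice, which the protocol does not spell out. The clear error is confined to withdrawals and losses.

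**Precision.** One might also infer that the interval is wrong because assumed non-falls are treated as observed. The simulation shows no material error. The analysed variable is a 0/1 indicator with a valid binomial variance, and the problem is bias.

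**Direction.** Nothing in the protocol predicts that the rule will favour zoledronic acid. If the drug lowers mortality, as Section 3.2 hypothesises, the placebo arm is observed for less time and the bias runs against the drug. More dropout on zoledronic acid would reverse it.

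**Existing safeguards.** The per-protocol rerun in Section 13.8 drops withdrawals and losses, but it selects participants who were qualified for and received both infusions. Questions at withdrawal (Section 7.2) and next-of-kin interviews (Section 9) recover falls before exit, not after it. These help a little and do not replace an analysis that accounts for time at risk.

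**Conclusion.** The concern holds for withdrawals and losses to follow-up. The rule understates absolute fall risk whenever there is early exit. It biases the relative risk only when early exit differs between arms, towards fewer falls in the arm observed for less time.

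The size is modest. A 2-point gap around the planned 5% dropout moves the relative risk by about 1%. A 5-point gap moves it by 2-3%. That gap, at 15% against 20%, needs dropout at or above the top of the range in the cited trials, or deaths counted as exits. With equal exit and no true effect there is no bias in the relative risk.

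These figures rest on assumed fall risks of 30-70%, a constant hazard, evenly spread exits and exit unrelated to fall risk. The protocol supplies none of these. The change is still worth making, because the rule is written into the plan, affects a stated secondary objective and can be replaced cheaply.

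**What to change.** In Section 13.6:

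1. Delete the assumption of no fall for participants who withdraw or are lost.
2. Analyse the first six-month contact interval with a reported fall by a discrete-time model (complementary log-log link, interval indicators, treatment), censoring withdrawals and losses at the last completed contact.
3. State how death is handled: as a competing event if the target is the 48-month risk, or as censoring if the target is a hazard ratio while alive. Censoring deaths and then quoting a 48-month risk would describe a population in which nobody dies. With F = 50% and 10% deaths, that gives 50% against an actual ever-fall proportion of 0.90 × 0.5 + 0.10 × 0.2787 = 47.8%.

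In Section 13.8, extend the extreme-scenario sensitivity analysis from the primary outcome to falls.

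The cost is protocol or SAP wording and slightly more analysis work. Falls are already asked about at each contact, so no new data are needed. The downside is that censoring assumes dropout is unrelated to fall risk, which may fail if frailer participants leave early. The extended sensitivity analysis addresses that.

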13.7. Safety analysis

All participants who receive at least one infusion will be included in a safety analysis. The occurrence of adverse events by the end of follow-up will be analyzed as the number of events and the number and percent of participants reporting at least one event. These data will

Study Name: The Fragility Fracture Trial
Version No: 2
Date: 2020-10-04
EudraCT No: 2019-004766-17

be presented by study group, seriousness, and causality (suspected/not suspected relation to study medication). The study groups will be compared using Fisher's exact test. For post-infusion symptoms occurring ≤ 3 days after infusion, data will be presented for both infusions in total and for events reported to have occurred ≤ 3 days after each infusion. In addition to specific adverse events, the composite safety outcomes of any adverse event, any serious adverse event, any serious adverse drug reaction, any unexpected adverse drug reaction, and any suspected unexpected serious adverse reaction will be reported. Laboratory values of serum calcium (low, <2.2 mmol/l; normal, 2.2-2.6; high, >2.6)⁶² will be analyzed in a shift table from before the first to before the second infusion. The number and percent with severe renal impairment (estimated glomerular filtration rate <35 ml/min/1.73m²) at Follow-Up Visit 1 will be presented. The mean and standard deviation change in estimated glomerular filtration rate from before the first to before the second infusion will be presented and compared between the groups using an independent-samples *t* test (Satterthwaite approximation of degrees of freedom).

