Given the high incidence of non-hip, non-vertebral fractures, the high risk of recurrent fractures, and the seriousness of hip and vertebral fractures, which occur later in life than other types of fractures, it would be of high interest to study whether bone-protective therapy is effective in older adults who are selected solely for having a history of non-hip, non-

Study Name: The Fragility Fracture Trial
Version No: 2
Date: 2020-10-04
EudraCT No: 2019-004766-17

vertebral fracture, without prior assessment of bone mineral density. Increased treatment of this patient group is feasible because only around 10% of Swedish fracture patients aged 50 or older receive treatment.^{15,16}

Zoledronic acid is a well-known and well-studied bone-protective agent, which was approved in the European Union in 2005.¹⁷ Zoledronic acid reduces bone resorption and belongs to the bisphosphonate class.¹⁸ In three large clinical trials, zoledronic acid was shown to reduce the risk of clinical fracture in women with osteoporosis, in women with osteopenia, and in men and women with a hip fracture.^{19–21} Although a fourth trial conducted in men with osteoporosis did not show a significant effect of zoledronic acid on clinical fractures, this trial was smaller and it did show a significant effect on radiologically detected vertebral fractures.²²

The most common adverse effects of zoledronic acid are transient post-infusion symptoms (pyrexia, myalgia, headache, arthralgia, and influenza-like symptoms), which occur in about one third of patients in the first 3 days following an initial infusion.¹⁹ These symptoms are less common after subsequent infusions.¹⁹ Zoledronic acid and other bisphosphonates have been associated with two rare but serious adverse effects: atypical femoral fractures and osteonecrosis of the jaw.^{23,24} However, osteonecrosis of the jaw does not primarily occur in osteoporosis patients but in cancer patients, who receive much higher doses of zoledronic acid to reduce the adverse skeletal effects of cancer (e.g., bone metastases).²³ In osteoporosis patients, the incidence of osteonecrosis of the jaw is estimated to be 1 in 100,000 to 1 in 10,000.²³ Atypical femoral fractures are also rare, and they are typically reported after long treatment periods of 7 or more years.^{25,26} It should also be noted that no increased risk of these adverse events was reported in the four largest trials of zoledronic acid that have been conducted to date.^{20–22,26}

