13.10. Sample size and power calculations

The trial will enroll 2900 patients, of whom 227 will need to sustain a clinical fracture during follow-up for the study to achieve 90% power to detect a 35% reduction in clinical fractures with the log-rank test (2-sided significance level of 5%). This calculation assumes a 4-year fracture risk of 10% in the placebo group and an overall dropout rate of 5% (due to withdrawal or loss to follow-up, i.e., deaths excluded). The details of the calculation can be found in Appendix 1. Appendix 2 provides a table of required sample sizes under varying assumptions. As shown, the required sample size is sensitive to changes in the assumed hazard ratio and the assumed fracture risk in the placebo group, but it is relatively insensitive to changes in the dropout rate.

To put the assumptions of the sample-size calculation in perspective, we note that 3 of 4 previous large trials of zoledronic acid had 90% power,^{19,20,22} whereas the fourth had 80% power.²¹ Incomplete follow-up (deaths excluded) was observed in 4% of women with osteopenia (6-year follow-up),²¹ 8% of men with osteoporosis (1-year follow-up),²² 13% of women with osteoporosis (3-year follow-up),¹⁹ and 17% of hip fracture patients (1.9-year

Study Name: The Fragility Fracture Trial
Version No: 2
Date: 2020-10-04
EudraCT No: 2019-004766-17

median follow-up).²⁰ Three of the trials that were powered to demonstrate effects on clinical fractures, and these showed effects of 27%,²¹ 33%,¹⁹ and 35%.²⁰

The assumed 4-year fracture risk of 10% was derived from data about the Swedish population that we have previously collected from the Swedish National Patient Register. We selected adults in Sweden who were aged 65 to 85 years and who suffered an initial fracture of the arm or lower leg in 2006 (ICD-10-SE codes: S42, S52, or S82). There were 10,361 such individuals who were not prescribed bone-protective treatment over the next 4 years. Their mean age was 74.9 years and 73% were women. Over the 4 years, 10.0% (n=1028) suffered a new fracture at a different skeletal site. We expect the restriction of the analysis to fractures of a different skeletal site to lead to an underestimation of the incidence of new fractures, but the restriction is necessary to avoid counting the same fracture twice. The distribution of fractures by skeletal site was as follows:

1. 457 fractures of the hip
2. 148 fractures of the upper arm
3. 125 fractures of the lower leg and foot joint

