There are also risks involved in participating in this trial. One risk is that of adverse effects. As explained in the Introduction, zoledronic acid causes post-infusion symptoms in about a third of patients, but these symptoms are transient and less common after the second infusion.¹⁹ More serious are the adverse effects of atypical femoral fractures and osteonecrosis of the jaw. These effects are rare, however.^{23,24} It should also be noted that increased risks of these events were not reported in four previous large trials of zoledronic acid.^{20–22,26} In these trials, zoledronic acid was given at more frequent intervals than is planned in our trial, which reduces the risk of adverse effects in our trial.

Another aspect of ethical concern is that some of the patients in the placebo group likely would have received bone-protective treatment if they had not been included in this trial. However, only about 10% of fracture patients receive treatment,^{15,16} and there is currently no standard treatment for fracture patients who (as the patients in the current trial) do not have a hip or vertebral fracture.

There is also a risk of invasion of privacy because we intend to contact potential participants through the registers, primarily the Swedish Fracture Register. However, individuals registered in the Swedish Fracture Register have agreed to the use of their data in research. In summary, we consider the benefits of conducting this study to outweigh the risks, making the trial ethical to perform.

Study Name: The Fragility Fracture Trial
Version No: 2
Date: 2020-10-04
EudraCT No: 2019-004766-17

18. References

- 1 Socialstyrelsen. Statistikdatabas för diagnoser i slutna vården. https://sdb.socialstyrelsen.se/if_par/val.aspx. Accessed 29 Nov 2019.
- 2 Socialstyrelsen. Statistikdatabas för diagnoser i specialiserad öppen vård. https://sdb.socialstyrelsen.se/if_paro/val.aspx. Accessed 29 Nov 2019.

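### Section 13.7 compares adverse events between arms by Fisher's exact test alone; a risk difference and relative risk with 95% confidence intervals should be added

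*Protocol*

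**What the plan says.** Section 13.7 defines the safety population ("All participants who receive at least one infusion will be included in a safety analysis"). It says that adverse events will be "analyzed as the number of events and the number and percent of participants reporting at least one event", broken down by study group, seriousness and causality. The between-arm comparison is one sentence: "The study groups will be compared using Fisher's exact test". The composites, such as any adverse event and any serious adverse event, are to be reported alongside the specific events.

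The opening of Section 13 supplies the reading rule: "P-values <0.05 will be considered statistically significant, unless otherwise specified", and "All statistical hypothesis tests that can be two-sided will be two-sided".

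Three laboratory items in 13.7 are handled otherwise. Change in estimated glomerular filtration rate gets means, standard deviations and a t test. Serum calcium gets a shift table. Severe renal impairment at Follow-Up Visit 1 gets a number and percentage. None of these names an interval either.

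Section 13.6 is fuller on benefit. It specifies hazard ratios with 95% confidence intervals, 95% intervals for numbers needed to treat, and a relative risk with a 95% interval for falls.

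**The concern.** Falls and the safety outcomes in Section 7.4 are the same kind of data: whether a participant had at least one event during follow-up. For falls the protocol plans an estimate with its precision. For harms it plans a p-value beside the raw counts.

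A p-value is the weaker summary here. Many of the listed harms are likely to be uncommon, and the trial was sized for fractures. A result above 0.05 could then come from a harmless drug or from too few events, and the p-value cannot separate the two. An interval can, because its upper limit says how much harm the data still allow. The trial's purpose is to support treating patients without bone densitometry, so the balance of benefit against harm needs that limit.

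**Working it through.** **Inputs.** Section 13.10: "The trial will enroll 2900 patients, of whom 227 will need to sustain a clinical fracture during follow-up". Section 10: 1:1 allocation. This gives 2900/2 = 1450 per arm, if nearly all randomised patients are infused. Section 13: two-sided test at 0.05. The protocol gives no power for any safety outcome and no placebo risk for most of them, so the placebo risks below are assumptions.

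**The protocol's own sample size.** Events: 4(1.960 + 1.282)²/(ln 0.65)² = 226.5, so 227. Treated risk: 1 − 0.90^0.65 = 0.06619. Patients: 227/[(0.10 + 0.06619)/2] = 2732; 2732/0.95 = 2876, rounded to 2900. This reproduces and is not in question.

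**Smallest split that reaches significance when one arm has no events.** For k v 0 with equal arms, the two-sided Fisher p is 2 × C(1450,k)/C(2900,k), close to 2 × (1/2)^k:

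- 4 v 0: p = 0.125
- 5 v 0: p = 0.062
- 6 v 0: p = 0.031

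So a very rare harm needs at least 6 v 0. Six in 1450 is 0.41%.

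**Power of Fisher's test to detect harm.** This is the sum, over all pairs of event counts, of the product of the two binomial probabilities, counting only tables with p at or below 0.05 in the harmful direction; 1450 per arm.

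| Assumed placebo risk | 1.5-fold increase | Doubling | Tripling |
|---|---|---|---|
| 0.1% | 1% | 2% | 9% |
| 0.5% | 9% | 27% | 73% |
| 1% | 18% | 55% | 97% |
| 2% | 36% | 87% | about 100% |
| 3% | 53% | 97% | about 100% |
| 5% | 78% | over 99% | about 100% |

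With 1377 per arm (2900 × 0.95/2), power is 0 to 3 percentage points lower.

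**What an interval would add.** Take 44 v 29 events in 1450 per arm (3.03% v 2.00%), an illustrative result:

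- Fisher p = 0.096
- Relative risk = 44/29 = 1.52
- SE of its logarithm = √(1/44 − 1/1450 + 1/29 − 1/1450) = 0.236
- 95% CI = exp(0.417 ± 1.96 × 0.236) = 0.95 to 2.41
- Risk difference = +1.03 percentage points, 95% CI −0.12 to +2.22 (Newcombe)

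With 7 v 7 events, p = 1.00, yet the relative risk of 1.00 has a 95% CI of 0.35 to 2.84. In both cases the p-value is not significant while more than a doubling remains compatible with the data.

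**An arm with zero events.** The one-sided 95% upper bound on that arm's risk is 1 − 0.05^(1/1450) = 0.21%. As the limit of a two-sided 95% interval it is 1 − 0.025^(1/1450) = 0.25%.

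**The case against.** The strongest reply is that this is a matter of detail. Fisher's test is valid for sparse counts, and nothing in 13.7 excludes intervals. A statistical analysis plan, not shown here, could add them without contradiction. The counts and denominators will be published, so a reader can compute any contrast. The rarest harms are also followed case by case, through causality assessment and SUSAR reporting (Section 8), and several are traced in registers over ten years (Section 7.4). With 1450 per arm no method resolves events that rare; the zero-event bound of 0.21% is for one arm and is not a comparison.

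All of that is true, and it limits the severity. What stands is that 13.7 does fix a between-arm method, in a protocol detailed enough to specify p-value rounding and variance estimators. That method is less informative than the one the protocol chose for falls.

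Three stronger readings are tempting, and the documents do not support them:

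- A reader might infer that a non-significant result is to be taken as no harm. No section sets that rule. Section 17 does say of earlier trials that "It should also be noted that increased risks of these events were not reported in four previous large trials of zoledronic acid", but it also lists these events as adverse effects and calls them rare.
- A reader might infer that the test would miss most harms that matter. That depends on the assumed rates. Power for a doubling is 87% at a placebo risk of 2% and 97% at 3%. For post-infusion symptoms, with about one third affected on active drug (Section 2) against an assumed 10% on placebo, it is close to 100%.
- A reader might multiply the jaw osteonecrosis figure in Section 2 ("In osteoporosis patients, the incidence of osteonecrosis of the jaw is estimated to be 1 in 100,000 to 1 in 10,000") to show that large relative increases go undetected. In context that figure appears to describe treated patients, and it has no time unit. It cannot serve as an untreated four-year risk.

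**Conclusion.** The point holds as a minor, inexpensive improvement. For binary adverse events, 13.7 names Fisher's test as the only between-arm comparison and gives no estimate or interval. At 1450 per arm the test is weak for uncommon harms: it detects a doubling with 27% power at an assumed placebo risk of 0.5% and 55% at 1%, and a 1.5-fold increase with 18% at 1% and 36% at 2%. It is adequate for a doubling from about 2% upwards.

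These figures rest on placebo risks that the protocol does not give, and on nearly all randomised patients being infused. The conclusion does not need any one of them: at whatever rate occurs, the p-value leaves unsaid how much harm is still compatible with the data. The sample size and the efficacy analysis are unaffected.

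**What to change.** In Section 13.7:

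- For each pre-specified binary safety outcome and each composite, give the risk difference and relative risk with 95% confidence intervals, using an exact or score method where counts are sparse.
- Where an arm has no events, give the exact upper 95% bound on its risk.
- Keep Fisher's p-value as a descriptive addition, and state that p≥0.05 is not evidence of no increased risk.

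The cost is a few sentences and a few lines of R, with no extra patients or data. The downside is a slightly longer analysis and a report that shows openly that rare harms have not been excluded.
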